13	Data Management	19
14	Translational research	19
15	Publication Policy	20
16	Insurance/Indemnity	20
17	Financial Aspects	20
18	References	21

1. Study Synopsis

Title of clinical trial	The study of aerosol generation with the droplet reduction mouthpiece during esophagogastroduodenoscopy
Principal Investigator	[name]. [name]
Medical condition or disease under investigation	Aerosol generation with the droplet reduction mouthpiece during endoscopy procedures
Purpose of clinical trial	To investigate the effect of droplet reduction mouthpiece on aerosol particle generation during esophagogastroduodenoscopy
Primary objective	Generation of aerosol particles by esophagogastroduodenoscopy with the droplet reduction mouthpiece
Secondary objective (s)	None
Trial Design	Prospective interventional study
Sample Size	80 patients undergoing elective upper GI endoscopy
Summary of eligibility criteria	Patients undergoing elective upper gastrointestinal endoscopy
Maximum duration of treatment of a subject	Not applicable
Version and date of final protocol	Version 2: 04 March 2021
Version and date of protocol amendments	Not Applicable

2. Background and rationale

Gastrointestinal (GI) endoscopy is one of the most commonly performed invasive procedures in clinical practice. Health care workers (HCW) at the endoscopy unit are at constant occupational risk for many infectious diseases as they perform daily procedures that are believed to generate aerosol and droplets, which may harvest respiratory pathogens. The size of particles determines the time of suspension in air and the distance of transmission. Currently, droplets are defined by a particle size larger than 5 µm in diameter while particles below 5 µm diameter are referred to as aerosols (1). Generally, all endoscopic procedures are considered potentially aerosol generating (2). Current guidelines recommend using high-level protection with N95 mask, FFP2 or FFP3, gloves, face shield and gown for high-risk patients during endoscopic procedures (3, 4). A growing number of scientific reports confirm that esophagogastroduodenoscopy is an aerosol-generating procedure (5, 6). A number of approaches to decrease the amount of aerosol generated have been reported including, for instance, the use of dental sucker in the oral cavity for continuous suction during the procedure or placing patients with their heads covered by a plastic enclosure, "endoscopic shield" (5, 6). Nevertheless, either use of the dental sucker or endoscopic shield may be less comfortable for patients and requires time and personnel and may therefore also be inconvenient for HCW.

During esophagogastroduodenoscopy (EGD), a hard-plastic mouthpiece is used to protect the endoscope from being bitten and to enable its smooth insertion. In September 2020, the droplet reduction Mouthpiece "B1" (Mouthpiece MPC-ST GMDN:62534 Generic name: Endoscopic bite block, basic, reusable) was launched by Fujifilm Corporation, Tokyo, Japan and imported to Europe by Fujifilm Europe. The droplet reduction mouthpiece is used in the same way as the conventional mouthpiece but differs from current mouthpieces by the inclusion of a sponge rubber incorporated into the mouthpiece orifice, and a drape shield specifically created to catch and reduce the droplets emitted by the patient during upper gastrointestinal endoscopy. This newly developed mouthpiece is considered for application during routine endoscopy at our facility during the COVID-19 pandemic, helping to minimize the risk to HCW and patients from becoming infected with COVID-19 and various other pathogens. However, there is a lack of scientific evidence on the amount of aerosol reduction with the modified mouthpiece when upper GI endoscopy is being performed.

The aim of the present study is to quantify the generation of aerosols when performing upper GI endoscopy with the modified mouthpiece. We intend to quantify the number of particles in the air near the patient. The duration of therapeutic upper gastrointestinal endoscopies can vary extremely. To avoid risk of imbalance in procedure durations, we are limiting the protocol to standard diagnostic EGDs. We assume that aerosol generations during short procedures can be extrapolated to longer procedures and hence this should not invalidate the findings.

3. Trial objectives and Design

3.1 Trial objectives

To perform a study to quantify the number of aerosol generation during EGD, using the droplet reduction mouthpiece, in the phases of COVID-19 pandemic.

[figure not shown]
3.2 Primary endpoints

Generation of aerosol particles by esophagogastroduodenoscopy with the droplet reduction mouthpiece.

3.3 Secondary endpoints

None

3.4 Trial Design

3.5 Trial Flowchart

Study Procedures	Timing
PCR testing on nasopharyngeal swab 24 hours prior to the test performed and negative	Day -2 or day -1
Informed consent	Day -2, -1 or Day 0
EGD	Day 0
Measurement of aerosol generation	Day 0

4 Selection and withdrawal of subjects

4.1 Inclusion criteria

- Aged >18 years old;
- Male or female patients;
- Patients undergoing elective standard diagnostic EGD;
- Negative PCR on nasopharyngeal swab 24 or 48 hours prior to the test;
- No anatomical deformity of nose and throat, no known diseases of nose and throat;
- Signed informed consent.

4.2 Exclusion criteria

- Females who are pregnant or lactating.

4.3 Expected duration of trial

The duration of this protocol is estimated at 3 months.

4.4 Recruitment of subjects

Patients are recruited from the gastroenterology clinic at the University Hospitals Leuven. Patients undergoing elective EGD will be invited to participate in the study.

5. Trial Procedures

5.1 Preparation room and patient

5.1.1 Room

The room is also equipped with an air particle counter (Lasair particle measure counter). A plastic tube, connected to the inlet of the counter, is placed within 10 cm from the mouth of the patient once the patient is set up in the room. The counter takes 1-minute air samples to quantify particles of 0.3, 0.5, 0.7, 1, 5 and 10 μm (6). Measurements of particle counts occur right before the endoscope insertion and 1, 3, 5, 10 and 15 minutes after the start of endoscopy, as well as after the completion of endoscopy. If the endoscopy is terminated before all measurements are done, the remaining measurements at time point 10 minutes and/or 15 minutes will be dropped.

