5.2 Esophagogastroduodenoscopy

A conventional gastrointestinal videoscope will be orally inserted into the stomach to observe the upper gastrointestinal tract. During the examination, patients will be placed on their left side. EGD for all patients will be performed by one endoscopist and one assistant nurse.

Premedication with anticholinergic agents or glucagon will not be used. Lidocaine (8%) will be sprayed into the posterior pharynx of all patients before insertion of the endoscope to reduce the gag reflex. Then, midazolam (0-5 mg) and pethidine (0-50 mg) can be administered intravenously for sedation, depending on the expected difficulty of the procedure and the anxiety level of the patient. Adequate monitoring of vital signs and oxygen saturation is performed throughout the examination.

6 Assessment of aerosol generation

Particle counts per cubic feet for each particle size will be measured prior to start of the procedure, and 1, 3, 5, 10 and 15 minutes after the start of endoscopy, as well as after the completion of endoscopy. If the endoscopy is terminated before all measurements are done, the remaining measurements at time point 10 minutes and/or 15 minutes will be dropped. The primary outcome will be to assess the changes of aerosols before, during, and after endoscopy and compare their trends in using droplet reduction mouthpiece and conventional mouthpiece groups. The changes in particle counts over time will be described and a random effect of repeated measures will be used in models to examine the effect of new mouthpiece.

7 Safety reporting

At the study visit, the investigator will determine whether any adverse events have occurred. The patient will be questioned in a general way and no specific symptoms will be suggested. If any adverse events have occurred, they will be recorded and we will act accordingly.

Since this is an Investigator driven study, the Sponsor is the Investigator and it should be interpreted as such.

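### Isolated 1-minute counts at fixed clock marks, with windows undefined and none tied to insertion or withdrawal, leave about half of a 6-minute EGD and more of any longer one unsampled

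*Combined protocol and SAP*

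**What the plan says.** Section 5.1.1 gives the sample length and size channels: "The counter takes 1-minute air samples to quantify particles of 0.3, 0.5, 0.7, 1, 5 and 10 μm". It gives the times as "Measurements of particle counts occur right before the endoscope insertion and 1, 3, 5, 10 and 15 minutes after the start of endoscopy", with one further count "as well as after the completion of endoscopy". If the procedure ends early, "the remaining measurements at time point 10 minutes and/or 15 minutes will be dropped". Section 6 repeats this schedule.

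Section 6 also states the target: "The primary outcome will be to assess the changes of aerosols before, during, and after endoscopy", with the trends compared between the two mouthpiece groups in a repeated-measures model with a random effect. Section 2 says the aim is to quantify aerosol generation while upper GI endoscopy is performed, and on procedure type, "we are limiting the protocol to standard diagnostic EGDs".

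Four things are not stated:
- whether a 1-minute sample starts at, is centred on, or ends at its mark;
- how soon after the end the completion sample is taken;
- how long an EGD is expected to last;
- whether the counter can take samples one straight after another.

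**The concern.** The marks follow the clock, not the events of the procedure. Section 5.2 says that lidocaine "will be sprayed into the posterior pharynx of all patients before insertion of the endoscope to reduce the gag reflex", so the plan itself links insertion with a reflex that could plausibly expel droplets. Yet whether the insertion minute is sampled depends on a convention the protocol leaves open. Withdrawal is sampled only when it happens to coincide with a mark. Mouthpiece removal is sampled only if the undefined completion sample happens to include it.

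Section 2 describes the new mouthpiece as having a sponge in its orifice and a drape to catch emitted droplets. If emission comes in short bursts, a patient's contribution to the comparison depends partly on whether a burst fell near a sampled minute. That is avoidable noise in a study of 40 per arm with no power calculation (section 8.1), and minutes not recorded during the EGD cannot be recovered later.

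**Working it through.** The plan states no coverage or precision figure, so there is none to reproduce.

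**Inputs.** From section 5.1.1: sample length 1 minute; marks t = 1, 3, 5, 10, 15; baseline and completion samples outside the procedure. Assumed, because the documents do not give it: EGD duration D. The drop rule names only the 10- and 15-minute points, which suggests that about 5 minutes or more was expected.

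**Step 1: share of the EGD sampled.** Add up the overlap of each window with the interval from 0 to D, counting marks with t ≤ D, and divide by D. Three conventions are tried: the window runs from t to t+1 (starts), t−0.5 to t+0.5 (centred), or t−1 to t (ends).

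| D (min) | Sampled minutes: starts / centred / ends | Unsampled share |
|---|---|---|
| 3 | 1 / 1.5 / 2 | 67 / 50 / 33% |
| 4 | 2 / 2 / 2 | 50% |
| 5 | 2 / 2.5 / 3 | 60 / 50 / 40% |
| 6 | 3 / 3 / 3 | 50% |
| 7 | 3 / 3 / 3 | 57% |
| 8 | 3 / 3 / 3 | 62.5% |
| 10 | 3 / 3.5 / 4 | 70 / 65 / 60% |
| 12 | 4 / 4 / 4 | 67% |
| 15 | 4 / 4.5 / 5 | 73 / 70 / 67% |
| 20 | 5 / 5 / 5 | 75% |

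A bound gives the same answer. At most 3 minutes are sampled when D is 5 to under 10, at most 4 when D is 10 to under 15, and at most 5 from 15 on. Since 3/6 = 50%, 4/10 = 40% and 5/15 = 33%, any EGD longer than 6 minutes is less than half sampled.

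**Step 2: the minutes at either end.** The first minute is sampled 0% (starts), 50% (centred) or 100% (ends). The last minute is not sampled under any convention at D = 7, 8, 12 or 20. At the other durations in the table it is sampled fully, half or not at all, depending on the convention.

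**Step 3: within-patient precision.** Assume minute counts with constant mean and variance and lag-1 autocorrelation ρ (AR(1)). For a mean over n minutes in a set S, variance = σ² × (1/n²) × ΣΣ ρ^|i−j|, summed over all i and j in S. Compare the sampled minutes with all D minutes.

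Example with D = 6, ρ = 0.3 and windows starting at the mark (minutes 2, 4 and 6):
- sampled: [3 + 2(2×0.3² + 0.3⁴)]/9 = 3.376/9 = 0.375;
- every minute: [6 + 2(5×0.3 + 4×0.3² + 3×0.3³ + 2×0.3⁴ + 0.3⁵)]/36 = 9.919/36 = 0.276;
- ratio: 1.36.

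| D (min) | ρ = 0 | ρ = 0.3 | ρ = 0.6 |
|---|---|---|---|
| 6 | 2.00 | 1.36 | 1.12 |
| 8 | 2.67 | 1.76 | 1.36 |
| 10 | 3.33 | 2.16 | 1.60 |

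If windows end at the mark, the 6- and 8-minute rows are unchanged and the 10-minute row becomes 2.50, 1.58 and 1.14. The documents do not give ρ; the values show a range.

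**The case against.** Several stronger readings are tempting, and the documents do not support them.

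- *Most of every EGD is unmeasured.* Not shown. At 6 minutes or less the unsampled share runs from 33% to 67%, and procedures of 5 to 6 minutes are compatible with the drop rule.
- *Insertion is never measured.* True only if windows start at the mark. If they end there, the first minute is fully sampled. The supported defect is the undefined window.
- *The counter could simply record every minute.* This is an inference from "The counter takes 1-minute air samples to quantify particles" and from the tube already lying near the mouth. Consecutive sampling is stated nowhere.
- *A burst between marks is lost.* Not necessarily. Section 2 says particle size governs suspension time, and four of the six channels are at 1 μm or below, so a burst may still raise the next count. For that reason no probability of a missed burst is offered here.
- *The comparison is biased, or the aim cannot be met.* Both randomised arms share the schedule, so the gaps alone do not favour either. Fixed-time repeated measures can describe change and trend, and section 8.1 calls the study descriptive. Nothing shows that the arms differ mainly in the unsampled minutes, since the sponge and drape form part of the mouthpiece throughout.

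The precision ratios also concern within-patient variance only. Without the between-patient variance they cannot be turned into a loss of power for 40 versus 40. Comparability with the cited dental-sucker study may explain the marks, but a continuous record would contain those same marks.

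What stands is that sampling is sparse, its windows are undefined, and it is not anchored to the events of the procedure.

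**Conclusion.** The concern holds as a loss of information. At most five minutes are sampled during any EGD. The unsampled share is half at 6 minutes and more than half beyond that under every window convention, and coverage of insertion and withdrawal is left to convention or coincidence. For EGDs of 6 to 10 minutes, the within-patient variance of the procedure mean is about 1.1 to 3.3 times that of every-minute recording (autocorrelation 0.6 to 0, windows starting at the mark), and short peaks may be missed or blunted. Duration, autocorrelation and the AR(1) form are assumptions. The coverage figures need only the schedule and a duration. It should be changed before recruitment if the counter permits, because the gain is cheap, but it does not invalidate the randomised comparison.

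**What to change.** First confirm that the counter can take consecutive 1-minute samples.

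**If it can**, amend sections 5.1.1 and 6 as follows:
- Record back-to-back 1-minute samples from before insertion until a fixed, stated number of minutes after mouthpiece removal.
- Time-stamp scope insertion, scope removal and mouthpiece removal.
- Keep the planned time-point analysis, read from the same record.
- Add the mean count per minute from insertion to scope removal, and report the insertion, scope-removal and mouthpiece-removal minutes separately.

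**If it cannot**, state when each window starts and when the completion sample is taken, and tie one sample to insertion and one to withdrawal.

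The cost is a short amendment, three time stamps and more data rows, for example 10 in-procedure samples in place of 3 or 4 for a 10-minute EGD. Neither route adds a patient procedure.

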5.1.2 Patient

Before the investigations, all patients need to have a negative SARS-CoV-2 test. Eligible patients will be randomly assigned to one of the following groups: the group using the droplet reduction mouthpiece, or the group using the conventional mouthpiece for EGD. Randomization will be generated via an online randomization program (www.randomization.com).

5.2 Esophagogastroduodenoscopy

A conventional gastrointestinal videoscope will be orally inserted into the stomach to observe the upper gastrointestinal tract. During the examination, patients will be placed on their left side. EGD for all patients will be performed by one endoscopist and one assistant nurse.

Premedication with anticholinergic agents or glucagon will not be used. Lidocaine (8%) will be sprayed into the posterior pharynx of all patients before insertion of the endoscope to reduce the gag reflex. Then, midazolam (0-5 mg) and pethidine (0-50 mg) can be administered intravenously for sedation, depending on the expected difficulty of the procedure and the anxiety level of the patient. Adequate monitoring of vital signs and oxygen saturation is performed throughout the examination.

6 Assessment of aerosol generation

Particle counts per cubic feet for each particle size will be measured prior to start of the procedure, and 1, 3, 5, 10 and 15 minutes after the start of endoscopy, as well as after the completion of endoscopy. If the endoscopy is terminated before all measurements are done, the remaining measurements at time point 10 minutes and/or 15 minutes will be dropped. The primary outcome will be to assess the changes of aerosols before, during, and after endoscopy and compare their trends in using droplet reduction mouthpiece and conventional mouthpiece groups. The changes in particle counts over time will be described and a random effect of repeated measures will be used in models to examine the effect of new mouthpiece.

7 Safety reporting

At the study visit, the investigator will determine whether any adverse events have occurred. The patient will be questioned in a general way and no specific symptoms will be suggested. If any adverse events have occurred, they will be recorded and we will act accordingly.

Since this is an Investigator driven study, the Sponsor is the Investigator and it should be interpreted as such.

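### Sedation is discretionary and nothing in the readable text keeps the mouthpiece arm hidden when it is decided; recording the sedation plan before opening the allocation is a cheap improvement

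*Combined protocol and SAP*

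**What the plan says.** - **Sedation (section 5.2).** It is optional and variable: "midazolam (0-5 mg) and pethidine (0-50 mg) can be administered intravenously for sedation". The choice for each patient is a matter of judgement, made "depending on the expected difficulty of the procedure and the anxiety level of the patient". Other preparation in the same section is uniform: "Lidocaine (8%) will be sprayed into the posterior pharynx of all patients", and no patient receives anticholinergic agents or glucagon. Of the medications named, only sedation varies between patients.
- **Staff (section 5.2).** "EGD for all patients will be performed by one endoscopist and one assistant nurse". Nobody unaware of the arm is named for the sedation decision.
- **Allocation (section 5.1.2).** "Eligible patients will be randomly assigned to one of the following groups", and "Randomization will be generated via an online randomization program". Concealment, stratification and time of disclosure are not described.
- **Device (section 2).** The new mouthpiece differs by "the inclusion of a sponge rubber incorporated into the mouthpiece orifice, and a drape shield", so the two cannot look alike in use.
- **Outcome and model (section 6).** Particle trends are compared between the two mouthpiece groups, using a repeated-measures model with a random effect. No covariate is named, and sedation is not mentioned.
- **Size (section 8.1).** 40 patients per arm, without a power calculation.

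**The concern.** Randomisation balances underlying anxiety and procedural difficulty on average, so discretion alone is not a source of bias. The exposure arises only if the judgement is made with the arm known. A sponge in the orifice could alter how difficult the examination is expected to be, and a drape could alter anxiety. Those are the two grounds on which section 5.2 bases sedation.

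If sedation then differs by arm, and if it changes gagging or coughing and hence emission, part of the difference attributed to the mouthpiece would come from sedation. The purpose stated in the synopsis is the effect of the mouthpiece on aerosol generation. A reader judging the sponge and drape could be misled in either direction: more sedation in the device arm would flatter the device, and more in the control arm would hide a real reduction.

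The baseline particle count does not protect against this. It is taken just before insertion (section 5.1.1), whereas an effect on gagging or coughing would arise during the examination and so enter the change being compared.

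**Working it through.** **The plan's own figure.** 40 + 40 = 80 agrees with the synopsis. Section 8.1 gives no alpha, power, effect size or SD, so 80 cannot be derived from a formula.

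**Timing of disclosure.** Assignment appears in 5.1.2 and sedation in 5.2, but section order is a weak guide to time: 5.1.1 already describes counts taken after the endoscopy, and 5.1.2 goes back to the SARS-CoV-2 test, which the flowchart (3.5) places on day -2 or -1. The flowchart does not place randomisation at all. What can be said is that nothing readable prevents the arm being known.

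**Illustration 1: ratio for a device with no effect.** All inputs are assumptions: share of controls sedated p = 0.40; excess share sedated in the device arm d; proportional reduction in emission from sedation r = 0.25 or 0.50.

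Ratio = (1 − r(p + d)) / (1 − rp)

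| d | r = 0.25 | r = 0.50 |
|---|---|---|
| 0.10 | 0.875/0.900 = 0.972 | 0.750/0.800 = 0.938 |
| 0.20 | 0.850/0.900 = 0.944 | 0.700/0.800 = 0.875 |

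The direction reverses if controls are sedated more.

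**Illustration 2: false-positive rate.** Again assumptions: one summary log-count per patient, SD 1 within sedation level, 40 per arm, two-sided alpha 0.05, 50% sedated on average, no true device effect. Let d be the sedation imbalance and e the effect of sedation in SD units, with p1 = 0.5 + d/2 and p0 = 0.5 − d/2.

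- Shift: b = d × e
- Standard error: s = √[(1 + p1(1 − p1)e²)/40 + (1 + p0(1 − p0)e²)/40]
- Rejection probability: Φ(b/s − 1.96) + Φ(−b/s − 1.96)

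| d | e (SD) | b (SD) | False-positive rate |
|---|---|---|---|
| 0.10 | 0.5 | 0.05 | 5.5% |
| 0.20 | 0.5 | 0.10 | 7.2% |
| 0.20 | 0.8 | 0.16 | 10.2% |
| 0.30 | 0.8 | 0.24 | 17.1% |

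For d = 0.20 and e = 0.5: s = √(2 × 1.06/40) = 0.230 and b/s = 0.434, giving 0.072.

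For scale, the difference detectable with 80% power at 40 per arm is (1.96 + 0.84) × √(2/40) ≈ 0.63 SD, well above the shifts in the table.

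**The case against.** Several stronger readings are tempting, and the documents do not support them.

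- **That the arm is known when sedation is chosen.** A reader might infer this from the section order and the visible device. No section states it. Section 3.4 has no readable text and a figure is not shown, so the silence on blinding is a statement about the readable text only.
- **That any sedation difference is spurious.** If the device itself prompts more or less sedation, the difference is arguably part of the total effect of using it, and the plan never says that it wants only the direct effect of the sponge and drape. Section 2 also says that the new mouthpiece is handled like the conventional one, which weakens the case for altered expected difficulty. Both points stand. The remaining problem is that the two effects could not be told apart, because recording or reporting of sedation by arm is not described.
- **That the bias is large.** The documents give no sedation rate, no difference between arms and no effect of sedation on aerosol. The nearest statement is that lidocaine, given to everyone, reduces the gag reflex.
- **That chance imbalance in sedation is evidence of bias.** It is imprecision, for which the nominal 5% error already allows. It is at most a reason to stratify.

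The remedy can also be challenged: a plan recorded before allocation does not bind what is given afterwards, so stratifying on it cannot by itself remove differential sedation. That stands too. Its value is narrower: it fixes a true baseline factor and makes departures from it visible.

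**Conclusion.** The point holds as a cheap design improvement, not as a demonstrated bias. Sedation is discretionary, the devices are visibly different, and the readable text contains nothing that keeps the sedation judgement separate from knowledge of the arm or protects the comparison from it.

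On the assumptions above, a null device would show a ratio of 0.97 to 0.94 for a 10-point excess of sedation and 0.94 to 0.88 for a 20-point excess. The consequence is modest unless sedation both differs clearly by arm and strongly affects aerosol. Neither condition can be confirmed or excluded from the documents. The improvement is worthwhile whether the target is the total or the direct effect of the mouthpiece, and it must be made before enrolment because intent before allocation cannot be reconstructed later.

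**What to change.** Add to section 5.1.2, in words such as:

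> Once consent and eligibility are confirmed, the endoscopist enters in the eCRF whether sedation is planned (yes/no). The allocation is opened only after this entry. Randomisation is in blocks, stratified by planned sedation.

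Add to section 6:

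> Planned sedation is a fixed factor in the model. The agents and doses given, and departures from the plan, are recorded and reported by arm. The primary model is not adjusted for sedation given, because that is determined after allocation.

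Sedation practice is unchanged, and no dose or clinical rule is proposed. The change limits and exposes differential sedation without eliminating it, since departures after the allocation is opened remain possible.

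Cost: one eCRF field for the plan, two allocation lists instead of one, and both mouthpieces at hand until the allocation is opened. The agents and doses given must also reach the analysis data. An incomplete last block in each list may leave the arms slightly off 40 and 40.

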8.1 Sample size

The aim is to create a descriptive review on the aerosol contamination with the droplet reduction mouthpiece during endoscopy. As this is a descriptive analysis, no formal power calculation was performed. In total we will include 40 patients for endoscopy with the droplet reduction mouthpiece and 40 patients for endoscopy with the conventional mouthpiece. However, based on previous publications on aerosol generation with nasogastric intubation (7)

and on reduction of aerosol spread during upper endoscopy with a dental sucker (8), we consider this number adequate.

9 Quality assurance

Patient recruitment follows international consensus diagnostic standards. The aerosol counting device will be calibrated prior to and at 4-week intervals throughout the study.

10 Direct access to source data and documents

The investigator(s) and the institution will permit trial-related monitoring, audits, EC review and regulatory inspections (where appropriate) by providing direct access to source data and other documents (I.e. patients' case sheets, blood test reports, histology reports etc).

11 Ethics and regulatory approvals

The trial will be conducted in compliance with the principles of the Declaration of Helsinki (current version), the principles of GCP and in accordance with all applicable regulatory requirements. This protocol and related documents will be submitted for review to Ethics Committee of the University Hospitals Leuven and any subsequent protocol amendments will be submitted to this EC for approval.

The study can and will be conducted only on the basis of prior informed consent by the Subjects, or their legal representatives, to participate in the Study. The Participating Site shall obtain a signed informed consent form (ICF) for all patients prior to their enrollment and participation in the Study in compliance with all applicable laws, regulations and the approval of the Ethics Committee, if required. The Participating Site shall retain such ICFs in accordance with the requirements of all applicable regulatory agencies and laws.

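### No safety comparison by arm is planned, and a relatedness filter on eCRF entry, contradicted elsewhere in the protocol, would leave adverse event counts by arm not reliably comparable

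*Combined protocol and SAP*

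**What the plan says.** **Device and setting.** Section 2 describes the new mouthpiece as differing by "the inclusion of a sponge rubber incorporated into the mouthpiece orifice, and a drape shield", and says of its intended use: "This newly developed mouthpiece is considered for application during routine endoscopy at our facility". Under section 5.2, "midazolam (0-5 mg) and pethidine (0-50 mg) can be administered intravenously for sedation", so patients may or may not be sedated. Section 5.1.2 randomises them between the two mouthpieces.

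**Monitoring.** Section 5.2 adds: "Adequate monitoring of vital signs and oxygen saturation is performed throughout the examination". No section says that the readings are entered, summarised or compared.

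**Endpoints.** The synopsis and section 3.3 give no secondary objective or endpoint. The only model planned, in section 6, is for particle counts.

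**Finding adverse events.** At the study visit the investigator determines whether any have occurred; section 7 continues: "The patient will be questioned in a general way and no specific symptoms will be suggested". Section 7.3 widens this to enquiry at every patient contact and to events that staff observe themselves. Section 7.1.1 counts an unfavourable sign as an adverse event whether or not it is thought related to the product.

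**Entering adverse events.** Sections 7.2, 7.3 and 7.3.2 confine eCRF entry and reporting to events related to the study intervention. Sections 7.3.5 and 7.4 make the investigator responsible for having all safety events in the eCRF.

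**The concern.** The unit is considering the mouthpiece for routine use. A reader of the results will ask whether a sponge and drape at the mouth made any difference to oxygenation or to the conduct of the procedure. The trial is randomised and every patient is already monitored, so it could give an estimate. As written, it plans none.

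An adverse event table by arm could still be produced afterwards, but the filter makes it unsafe to read. The study-specific intervention is not defined. If it means the new mouthpiece, an event in the conventional arm has nothing to be related to, while the same event in the device arm may qualify. The person judging can see which mouthpiece is in use.

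A second gap touches the aerosol result. A mouthpiece or drape that is removed, swapped or fails without clinical consequence is not clearly an untoward medical occurrence under section 7.1.1, and no other section provides for recording it. Later counts would then describe a device no longer in place, and nobody could tell which counts those were.

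**Working it through.** **1. The entry rules side by side.**
- Sections 7.2, 7.3 and 7.3.2: related events only.
- Sections 7.3.5 and 7.4: all safety events in the eCRF. Section 7.3.5 also has every death reported to the sponsor regardless of cause.
- Section 7.3.1: every adverse event is graded for causality in five grades, including none and unlikely. The protocol does not say which grades count as related.

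The two sets cannot both be followed. Under the first, entry depends on an unblinded judgement with no stated cut-off.

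**2. What the filter can do to counts.** Let n = 40 per arm (section 8.1), p be a true event rate equal in both arms, and s be the share judged related. Expected entries are n × p × s. The extreme case is s = 1 in the device arm and s = 0 in the conventional arm:
- p = 5%: 40 × 0.05 = 2 entries against 0
- p = 10%: 40 × 0.10 = 4 against 0
- p = 20%: 40 × 0.20 = 8 against 0

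If s is equal in both arms, the expected gap is zero. The rates and shares are assumptions, as the documents give none. The gap can also run the other way if staff under-attribute events to the new device.

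**3. What 40 per arm can show once data are recorded.** There is no planned figure to reproduce. Section 8.1 sets "In total we will include 40 patients for endoscopy with the droplet reduction mouthpiece" and "40 patients for endoscopy with the conventional mouthpiece", and explains: "As this is a descriptive analysis, no formal power calculation was performed". At an assumed two-sided 5% level:
- No events in 40: one-sided 95% upper bound 1 − 0.05^(1/40) = 7.2%; two-sided upper limit 1 − 0.025^(1/40) = 8.8%.
- Difference in mean lowest saturation: 95% half-width 1.96 × SD × √(2/40) = 0.44 SD. For assumed SDs of 2, 3 and 5 points this is about 0.9, 1.3 and 2.2 points.
- Difference detectable with 80% power: (1.96 + 0.84) × SD × √(2/40) = 0.63 SD.
- Binary event, normal approximation: power is 13% for 5% against 10% (435 per arm needed for 80%) and 24% for 10% against 20% (199 per arm needed). Fisher's exact test gives lower power, 4% and 16%.

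**4. Device removal and particle counts.** Sections 5.1.1 and 6 take counts before insertion, at 1, 3, 5, 10 and 15 minutes, and after completion. They provide for dropping the 10- and 15-minute counts if the endoscopy ends early, but not for a change of mouthpiece while it continues.

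**The case against.** A reader might infer that safety rests on a single general question to a sedated patient. The documents do not support that. Section 7.3 adds enquiry at each contact and events seen by staff, and an observed sign can be an adverse event, so a desaturation on the monitor has a route to being recorded. Sedation is optional, and the time of the question relative to recovery is not stated.

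Two other strong readings also fail. That saturation is not used as data is only an inference from silence, because the eCRF fields are not listed. That the arms cannot be compared goes too far: allocation is randomised and events carry severity, causality and outcome, so a crude table is possible, though unplanned and open to differential recording.

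The scope argument has force. The stated objective is to quantify aerosol, the study calls itself descriptive, and section 2 says the mouthpiece is used in the same way as a conventional one. Nothing in the documents suggests an effect on oxygenation or that mouthpieces come off. Analysing counts by randomised arm is sound practice whether or not they do.

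It is also true that the 7.2% bound follows from 40 patients and is not improved by better recording, and that the documents do not say whether the monitor stores values. With one endoscopist and one nurse at the procedure, timed entries take some attention.

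What remains is the contradiction over what enters the eCRF, the scope for unequal recording, and the absence of any planned safety comparison or any provision for noting device failure.

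**Conclusion.** The point holds in a limited form. The protocol contradicts itself on which events are entered. Under its stricter rule, counts by arm could differ through recording alone. No safety comparison is planned, and recording of saturation or of device removal is not specified. The aerosol objective stands without a change, but a recommendation for routine use would lack reliable comparative safety evidence.

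The size of any recording bias cannot be derived from the documents. It ranges from nothing, if relatedness is judged alike in both arms, to the loss of all events in one arm. Better data would give an estimate with a 95% half-width of about 0.44 SD for lowest saturation. They would not prove equal safety, and they would say little about modest differences in event rates.

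This rests on the readable text describing no blinding (section 3.4 has no text in the copy reviewed) and on the eCRF not already holding these fields. The unequal-recording argument is strongest if the study-specific intervention means the new mouthpiece.

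**What to change.** 1. Reconcile sections 7.2, 7.3 and 7.3.2 with sections 7.3.5 and 7.4, so that events during the procedure are entered in both arms whatever the judged causality. Keep causality as a recorded attribute, and define the study-specific intervention.
2. Add eCRF fields for all 80 patients: saturation before the procedure and lowest saturation during it, procedure interrupted, and mouthpiece or drape removed, replaced or failed, with the time.
3. State in sections 3.3 and 8 that these are reported descriptively by randomised arm with confidence intervals.
4. Keep the primary aerosol analysis by randomised arm. Use the removal times to interpret later counts, not to reassign patients.

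The cost is a short amendment, a few fields, one descriptive table and a little extra data entry on the procedure day. If the monitor does not store readings, someone must note the lowest value at the time. No visit, procedure or change in clinical care is involved.
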